4 STUDY DESIGN

This study will utilize a multi-site, multi-level, and multi-component cluster randomized clinical trial design (Phase III) to assess interventions intended to address poor dental utilization (attendance) and untreated caries among 3-6 year old Medicaid-enrolled children attending well-child visits (WCV) in primary care settings. The focus is on addressing factors (determinants) at the socio-ecological levels of the child's environment: provider (pediatrician and nurse practitioner), parent/caregiver and practice/organization levels. Eighteen practices will be randomized to 2 arms for provider training and practice/organization level study intervention changes: A) provider-level CSM training, provision of oral health facts to parents, a prescription and a list of dentists accepting Medicaid + practice-level EMR changes for documenting oral health; B) AAP training with no prescription or list of dentists accepting Medicaid and no changes to the EMR. Arm A parents/caregivers will receive oral health facts and prescription to take their child to the dentist and improve oral health behaviors in the home, while Arm B parent/caregivers will receive usual AAP-based care for oral health. Each arm will consist of 9 practices (n= 18), 33 to 34 providers (n= 67), and 512 parent/caregiver and child dyads (n= 1024). Each parent/caregiver and child dyads will be recruited at the first WCV and then followed for two consecutive WCVs (for a 24 month duration or until the subject has completed 3 well child visits). Each provider will complete the didactic and skills training prior to enrolling any parent/caregiver and will participate in the study for a total of 24 months duration (includes initial and booster didactic and skills training: 3 months, WCV#1: 3 months, WCV#2: 3 months, WCV#3: 3 months). Data will be collected prior to WCVs, at WCVs, and follow-up visits.

Immediately after randomization of practices, recruitment will be rolled-out, i.e. parent/caregivers will be recruited during a 3-month period in 6 practices at a time, with recruitment at all 18 practices expected to be completed in 9 months. This strategy will maximize staff time and ensure that EMR integration of OH is complete at practices randomized to Arm A, and that providers receive the didactic and skills training prior to their practice's rollout.

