6.4 Assessment of Provider Compliance with Study Intervention

Arm A

Compliance with the provider-level intervention: The study staff's direct observation/audiotape of provider encounters will provide an assessment of whether providers communicated all 6 core OH facts and gave caregivers the prescription to go to the dentist along with list of area Medicaid-accepting dentists. It will also be used to assess whether the provider initiated the topic of the child's dental care with the caregiver and used appropriate communication skills. The exit questionnaire completed by parent/caregivers will assess whether their pediatrician/nurse practitioner communicated OH facts and gave them the prescription to go to the dentist and list of dentists (i.e. whether the caregiver received and understood the main points of the provider's oral health communication and the prescription they were being given). Compliance will also be verified with the numbered prescriptions and list of dentists to determine the total number given to each provider's enrolled caregivers.

Compliance with the practice-level intervention: The study staff will conduct EMR audits of all enrolled patients to determine whether the OH documentation was complete, i.e. provider documented whether or not they did the following during the OH encounter: 1) examined child's teeth for white or brown spots, 2) asked whether child had a dental visit in the past 12 months, 3) communicated core OH facts, and 4) gave caregiver a prescription to take their child to the dentist along with a list of Medicaid-accepting dentists in the area.

Arm B

Compliance with the provider-level intervention: Study staff evaluation of providers' OH encounters and parent exit questionnaires completed by a random 20% selection of each provider's enrolled patients will be used to assess whether Arm B providers communicated OH facts to identify possible contamination bias in delivery of the provider-level intervention (i.e. provider is giving caregivers provider-level intervention materials not associated with their assigned arm).

Study staff will perform EMR audits on a random 20% selection of each provider's enrolled patients to identify possible contamination bias in delivery of the practice-level intervention (i.e. providers are documenting patients' OH without having received the practice-level intervention).

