8.1.3 Provider

Provider-level measures include mediators (OH knowledge and self-efficacy), a confounder (socio-demographic characteristics), and evaluation of implementation/fidelity (observation and audiotape of OH encounters) and adoption & maintenance (i.e. percentage of enrolled patients given a prescription and list of dentists).

- Providers' OH knowledge and self-efficacy to perform OH activities will be assessed through pre- and post-tests (Appendix E) administered before and after the didactic education session prior to WCV #1 (T_{-1}) and booster sessions before WCV #2 (T_2).
- Providers' socio-demographic characteristics (Appendix E) will be collected at the didactic training sessions prior to WCV#1 (T_{-1}).
- As an evaluation of the implementation/fidelity of the intervention, providers' oral health encounters will be observed or audiotaped by study staff and evaluated using the ParentProvider Communication Checklist (Appendix E), the same standardized skills checklist used during the skills training session (T_0 , T_3 , and T_6).
- Parent/caregivers will evaluate their provider's oral health communication and delivery of prescription and list of dentists on the A3: Parent exit questionnaire (Appendix E) completed at WCVs #1 - #3 (T_0 , T_3 , and T_6). This is also an evaluation of implementation/fidelity.
- Providers' EMR documentation of prescriptions and lists of dentists given will be audited throughout the main trial (T_0 , T_3 , and T_6), based on study arm. The percentage of enrolled caregivers who received the prescription and list of dentists will be calculated as an

evaluation of providers' adoption and maintenance of the provider-level intervention and recorded on the EMR Audit of Practice form (Appendix E).

- Providers will complete structured interviews with a trained moderator on implementation barriers/enablers to evaluate best strategies for dissemination of the oral health intervention. The interviews will be conducted at the pediatric practices at a time convenient for the provider and will contain interview questions to assess relative advantage of the OH intervention, compatibility of the OH intervention with the needs of the adopters, complexity of the OH intervention, trialability, and observability. Interviews will be conducted using zoom if in-person interviews are not possible due to the current COVID-19 outbreak.

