will be modified by using a linear model (identify link) for GEE, modeling the mean response over time as a summary measure. These outcomes will each be tested for normality using the Shapiro-Wilk statistic; outcomes for which normality is violated will be transformed where appropriate or an alternative model used. For count outcomes (e.g., dft accumulated over time), we will use a loglinear model (log link) assuming a negative binomial or other appropriate (e.g., zero-inflated negative binomial) distribution. For proportion outcomes (e.g., dt/dft), we will use GEE with a logit link, assuming the proportion follows a beta binomial or zero-inflated beta binomial distribution (Albert et al 2014). Similarly, we will fit appropriate GEE models to test for the effect of each implementation strategy on the corresponding outcome (e.g., % prescriptions given as a measure of adoption). As in the dental attendance analysis, the intervention indicator as well as pertinent baseline variables will be included in the model. In addition, interaction terms (baseline variables by intervention) will be included to test for possible effect modification.

For secondary analyses, a GLIMMIX model approach will be considered as an alternative, which may more easily allow for more than one cluster level if needed. Another alternative approach is to model the repeated measurements (again using GEE or GLIMMIX) which will add an additional cluster level – namely, for individuals). Goodness of fit of alternative models will be compared using QIC for GEE (or AIC for GLIMMIX).

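### The between-arm test of prescriptions given cannot measure adoption, because Arm B gives none by design; under a logit link it is also not estimable unless contamination occurs

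*Combined protocol and SAP*

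**What the plan says.** Section 12.4 (Analysis of Secondary Outcomes) plans GEE models to "test for the effect of each implementation strategy on the corresponding outcome (e.g., % prescriptions given as a measure of adoption"). The share of prescriptions given is its named example of an adoption outcome. Shortly afterwards it adds: "As in the dental attendance analysis, the intervention indicator as well as pertinent baseline variables will be included in the model". The indicator is coded 1 for the bundled intervention and 0 for enhanced usual care, so the contrast is between arms. Baseline-by-intervention interaction terms are to be added as well.

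The link is set out just before this, for another class of outcome: "For proportion outcomes (e.g., dt/dft), we will use GEE with a logit link". For implementation outcomes the text says only that appropriate models will be fitted in a similar way.

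Section 4 describes the control arm as "B) AAP training with no prescription or list of dentists accepting Medicaid and no changes to the EMR". Section 6.2 confirms that Arm B receives no practice-level intervention.

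The measurement sections treat adoption differently from Section 12.4:

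- Section 8.1.3 audits prescriptions at all three well-child visits: "The percentage of enrolled caregivers who received the prescription and list of dentists will be calculated as an" evaluation of adoption and maintenance.
- Section 8.1.4 uses the percentage with all four EMR questions completed to evaluate adoption and maintenance in Arm A specifically.
- Sections 6.3.2 and 6.4 give Arm B monitoring another purpose, namely a baseline rate and a check for contamination, meaning that a "provider is giving caregivers provider-level intervention materials not associated with their assigned arm". EMR audits cover all enrolled patients in Arm A and a 20% sample in Arm B.

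**The concern.** Secondary objective 3 asks about adoption, reach, fidelity and maintenance. For prescriptions, the useful questions are what share of Arm A caregivers received one, how much that varied across the nine practices, and whether it held up to WCV #3, which Section 6.2 calls the maintenance visit. A comparison with an arm that was never given the prescription answers none of these.

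Two things are at stake. First, a very small p-value could be reported as evidence of adoption when it mainly reflects the design. Section 12.4 also feeds provider adoption into the tool kit for dissemination, so the result could be carried forward. Second, if no Arm B prescription is recorded, a logit model is separated, and standard software may print a huge coefficient with a small standard error instead of failing visibly.

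**Working it through.** The plan states no figure for the adoption outcome, so there is none to reproduce.

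**Inputs**

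- Arm B prescription rate by design: 0 (Section 4).
- Practices: 9 per arm. Children: 512 per arm (Section 4).
- Arm B audit: 20% of 512, about 102 records (Sections 6.3.2 and 6.4).
- Arm A prescription rate: not stated. Assumed 0.5 to 0.9.
- Arm B contamination rate: foreseen but not stated. Assumed 0 to 0.05.
- ICC for adoption: not stated. Assumed 0.04 (the Section 12.2 value for dental attendance). For the precision check, 0.20 is added because prescribing is a provider behaviour and may cluster more strongly.

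**Step 1: the null hypothesis.** With pB = 0 by design, the null pA = pB holds only if Arm A providers give no prescriptions either. Rejecting it shows only that pA exceeds zero. This is true under any link.

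**Step 2: the logit link.** With the arm indicator alone and independence working correlation, the arm coefficient is logit(pA) − logit(pB). As pB goes to 0, logit(pB) goes to minus infinity and the coefficient diverges. The baseline-by-intervention interactions are not identified either, because an arm without events carries no information on covariate slopes.

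**Step 3: what software reports.** A logit GEE was fitted to simulated data with 18 practices, about 57 children each, ICC 0.04 and 0 of 513 events in Arm B.

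| Assumed Arm A rate | Printed log odds ratio |
|---|---|
| 0.5 | 28.5 |
| 0.7 | 29.3 |
| 0.9 | 30.8 |

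Sandwich standard errors were 0.13 to 0.18 (0.15 to 0.21 with bias reduction). Almost all of each coefficient is the arbitrary Arm B intercept, about −28.6, at which the fit stopped. In the middle row Arm A had 347 of 513 events: ln(347/166) = 0.74, and 0.74 + 28.57 = 29.3.

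**Step 4: when the estimate is finite.**

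- With an identity link, the difference equals the observed Arm A rate: 0.46, 0.73 and 0.91 in single simulated datasets under the same three assumed rates.
- With a logit link and one Arm B event in 99 audited records, against 345 of 513 in Arm A: ln(345/168) − ln(1/98) = 0.72 + 4.58 = 5.30, standard error about 1.0. The size of this estimate is driven by a single contaminated record.

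**Step 5: chance of no Arm B events.** P(0) = (1 − pB)^n, ignoring clustering:

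| Assumed pB | n = 102 (20% audit) | n = 512 |
|---|---|---|
| 0.01 | 36% | 0.6% |
| 0.02 | 13% | below 0.01% |

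With low contamination, the 20% audit could therefore easily return zero. The exact one-sided 95% upper bound for 0 of 102 is 1 − 0.05^(1/102) = 2.9%.

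**Step 6: precision within Arm A.** At WCV #1, m = 512/9 = 56.9 per practice and the design effect is 1 + 55.9 × ICC, which is 3.24 at ICC 0.04 and 12.18 at ICC 0.20. The 95% half-width is 2.306 × √(p(1 − p) × design effect / 512), where 2.306 is the t quantile on 8 degrees of freedom:

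| Assumed p | ICC 0.04 | ICC 0.20 |
|---|---|---|
| 0.5 | ±9.2 points | ±17.8 points |
| 0.7 | ±8.4 points | ±16.3 points |
| 0.9 | ±5.5 points | ±10.7 points |

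These are wide but usable. Dropout at later visits would widen them somewhat.

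**The case against.** Four points can be made for the plan.

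- **The Arm A percentages are already planned.** A reader might infer that adoption is left without any estimate. That is not so. Sections 8.1.3 and 8.1.4 calculate the percentages from audits at all three visits, Section 12.4 plans summary statistics by group for secondary outcomes, and it offers repeated-measures models as an alternative. This stands. What Section 12.4 lacks for these measures is a statement that the Arm A percentage is the estimand, a clustered interval for it, and a specified within-arm comparison over visits.
- **The link is not fixed.** A reader might infer that the model can never yield a finite estimate. The logit link is stated for proportion outcomes and only implied for implementation outcomes. An identity link is finite, and one contaminated Arm B record makes the logit estimate finite. This stands, so non-estimability is conditional. Step 1 does not depend on the link.
- **The EMR is less clear-cut.** A reader might infer that EMR documentation is also a strict zero in Arm B. Section 6.2 says most University Hospitals practices already have the oral health questions, hidden from providers outside Arm A, and Section 6.3.2 audits Arm B for any oral health documentation. Near zero is an expectation to be checked. Prescriptions are also only an example in Section 12.4, so the point does not reach outcomes possible in both arms, such as the communication checklist.
- **The contrast is not wholly empty.** Allocation does not force Arm A providers to hand out prescriptions, and a very low Arm A rate would be hard to tell from Arm B. This stands to a limited extent: the contrast is a weak check that the arms received different care. It does not measure the degree or durability of adoption.

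**Conclusion.** The concern holds in a limited form. For study prescriptions, the planned between-arm test is uninformative about adoption under any link, because Arm B is zero by design and nothing in Section 12.4 restricts the model to Arm A. Under the logit link it is not estimable unless contamination produces at least one Arm B event. At an assumed 1% contamination rate, the 20% audit would find no event about 36% of the time, ignoring clustering. For completion of the four EMR questions the same argument applies less strictly, since the Arm B rate is expected to be near zero but is audited rather than assumed.

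The Arm A rates, contamination rates and ICCs used above are assumptions; the conclusion about the null hypothesis needs none of them. The consequence is confined to part of secondary objective 3. The primary analysis and the conduct of the trial are unaffected.

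**What to change.** In Section 12.4, for prescriptions given and for completion of the four EMR questions, replace the between-arm test with the following:

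1. The Arm A percentage at WCV #1, #2 and #3, as already defined in Sections 8.1.3 and 8.1.4, with practice-clustered intervals corrected for nine clusters. Section 12.4 already names a small-sample correction for the primary model. State the denominator at each visit.
2. A test of change over visits within Arm A, with practices as clusters, to address maintenance.
3. The Arm B percentage reported descriptively as contamination, with its audited denominator and an exact upper bound if the count is zero.

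Keep the between-arm GEE for implementation outcomes that can occur in both arms, and state the link for each.

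The cost is a change of wording in the analysis plan; the audit data are already being collected. The one drawback is limited precision from nine practices.

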Arm A will also have practice-level intervention that includes incorporation of four oral health questions into the practice EMR. As a result of this practice-level intervention, Arm A providers will receive EMR training to document the oral health encounter. The EMR training will occur simultaneously with the didactic and skills training sessions prior to WCV #1 and the booster session before WCV #2. Providers will receive an EMR training manual for documentation (more specifics on the EMR training manual will be detailed in the MOP; see Appendix D for EMR screenshots). While the majority of University Hospitals based practices have oral health questions incorporated in their EMR, the OH questions are hidden and will be available only to providers with appropriate training in practices in study Arm A. The other non-UH based practices randomized to study Arm A will have the OH questions incorporated prior to enrollment of caregiver and child participants.

Parents/caregivers of the providers and practices in Arm A are the recipients of the provider and practice level interventions. Parent/caregivers will receive CSM-based oral health facts, prescription to go to the dentist together with a list of Medicaid-accepting dentist.

Arm B

Providers will receive the standard AAP based didactic education in a 45-minute session prior to WCV #1 and a booster session prior to WCV #2. Arm B providers will not receive any CSMbased education, skills training or the practice-level intervention.

Parents/caregivers in this arm will receive the usual care for oral health as followed by the providers and practices currently.

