help reveal the importance of each of the multiple components of the bundled intervention. For example, we can estimate the proportion of intervention effect mediated by 'compliance' with regard to EMR documentation. A relatively high mediation proportion will suggest efficacy of the corresponding component.

We have previously developed a generalized causal mediation (GCM) analysis methodology and an accompanying R package (Albert & [name], 2011; Albert, Unpublished; Cho & Albert, Unpublished) which we will use to estimate and test each path effect and its proportion of the total intervention effect. The GCM method allows mediators and final outcomes of different types, including continuous, binary, and count (assumed to have normal, Bernoulli, and Poisson or negative binomial distributions, respectively). These options will accommodate the mediators and final outcome (dental attendance, summarized as a binary response) in our model. Each outcome (including mediators) is modeled using a generalized linear model that includes as covariates possible baseline confounders as well as causally preceding variables according to the causal model (as in Figure 4.2.1). The method uses an extended version of the mediation formula and assumes an extended version of the sequential ignorability assumption. (Albert et al., Unpublished) Bootstrap resampling is used to compute confidence intervals and a cluster bootstrap option is available to account for unexplained between-cluster (e.g. provider) variability.

Adjustment for Baseline Characteristics: Estimated intervention effects will be adjusted for the following baseline socio-demographic variables: child's age, race, and caregiver SES, education, and marital status.

Model Assumptions: We will assume that the probabilities of dental care receipt follow a logistic regression model with the included covariates and random effects. Per the standard approach, random effects will be assumed to be independent, normally distributed, and outcomes assumed conditionally independent given the random effects. If multiple random effects (e.g., for different cluster levels) are used, they will be assumed to be independent. For secondary outcomes, analogous assumptions, including the assumption of the correct link function, will be made.

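### A high proportion mediated by EMR documentation does not indicate that the EMR component works, because documentation partly stands in for delivery of the other components

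*Combined protocol and SAP*

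**What the plan says.** Section 12.4 (Final Analysis Plan) includes mediators intended to show how much each part of the bundle matters. Its example is that "we can estimate the proportion of intervention effect mediated by" compliance with EMR documentation, followed by the reading rule: "A relatively high mediation proportion will suggest efficacy of the corresponding component". The method "assumes an extended version of the sequential ignorability assumption", and each model "includes as covariates possible baseline confounders as well as causally preceding variables according to the causal model". No sensitivity analysis for the ignorability assumption is described.

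Three other places determine what this mediator measures.

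- **Access.** Under Section 6.2, most University Hospitals practices already hold the items, but "the OH questions are hidden and will be available only to providers with appropriate training in practices in study Arm A". Other practices have the items built only if they are in Arm A. Arm B receives no CSM education, "skills training or the practice-level intervention".
- **Content.** Section 6.4 lists four items: examining the teeth, asking about a dental visit in the past year, communicating the core facts, and giving the prescription with the dentist list. Documentation is complete when the "provider documented whether or not they did the following during the OH encounter", so a recorded no also counts.
- **Audit.** All Arm A charts are audited. For Arm B, "Study staff will perform EMR audits on a random 20% selection" of each provider's enrolled patients, to look for contamination.

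Section 8.1.3 also takes prescription adoption from the EMR audit.

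**The concern.** Randomisation supports the comparison of the whole bundle with enhanced usual care. It does not separate the EMR change from the facts, the prescription or the dentist list. To attribute part of the effect to documentation, the analysis must compare documented with undocumented children, and that contrast exists almost only inside Arm A, where nobody was randomised to be documented.

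Within Arm A, a provider who gives the facts and the prescription is plausibly also the one who completes the record, and two of the four items ask about exactly those acts. If delivery drives attendance and documentation follows delivery, documentation will appear to mediate even if the EMR change does nothing. Under the plan's rule, the EMR component would then be credited with the effect of the other components.

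**Working it through.** **Background figure.** The plan gives no figure for the mediation analysis, so the primary-outcome assumptions in Section 12.2 are used for calibration. They reproduce. Attendance of 0.46 against 0.30 at two-sided 0.05 and 80% power needs 144 per arm without clustering. Evaluable children per practice: 512 × 0.75 / 9 = 42.67. Design effect: 1 + (42.67 − 1) × 0.04 = 2.667. Recruitment: 144 × 2.667 / 0.75 = 512 per arm, as stated.

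**Set-up.** Let D be actual delivery of facts and prescription and M complete EMR documentation. Assume that the EMR has zero effect, that M = 0 in Arm B, and that the whole difference of 0.46 − 0.30 = 0.16 comes through D. Nothing else is adjusted for. With d = P(D=1) in Arm A, attendance is 0.30 + (0.16/d) × D. The mediation formula then gives:

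- indirect effect = E[Y in Arm A] − E[Y in Arm A, M=0] = (0.16/d) × (d − P(D=1 given M=0));
- apparent proportion mediated = 1 − P(D=1 given M=0) / d.

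**Worked case.** Take d = 0.80, with documentation complete in 90% of delivered and 20% of undelivered visits. P(M=0) = 0.80 × 0.10 + 0.20 × 0.80 = 0.24. P(D=1 given M=0) = 0.08 / 0.24 = 0.333. Proportion = 1 − 0.333 / 0.80 = 58%, against a true value of 0.

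All cases at 80% delivery (delivery and documentation rates are assumptions):

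| Documented if delivered / if not | P(M=0) | Delivered among undocumented | Apparent proportion |
|---|---|---|---|
| 90% / 90% | 0.10 | 0.800 | 0% |
| 90% / 70% | 0.14 | 0.571 | 29% |
| 90% / 50% | 0.18 | 0.444 | 44% |
| 90% / 20% | 0.24 | 0.333 | 58% |
| 95% / 5% | 0.23 | 0.174 | 78% |

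For delivery from 60% to 90%, with documentation related to delivery as in the last four rows, the range is 17% to 88%.

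**Sampling variation.** 1,000 trials per case were simulated (9 practices of 43 children per arm, ICC 0.04, logistic model on arm and M, true EMR effect zero). Trials with an estimated total effect of 0.02 or less were counted as not exceeding 50%. The estimated proportion exceeded 50% in 60.6% of trials at 90%/20%, 46.5% at 90%/50% and 80.6% at 95%/5%. With 5% documentation in Arm B and 90%/20% in Arm A, the median was 44% and 40.5% of trials exceeded 50%.

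**Near-determination by arm.** This is a separate effect. If Arm A documents a share p and Arm B none, the squared correlation of arm and M is p / (2 − p). At p = 0.90 it is 0.818, so the correlation is 0.90 and the variance inflation is 1 / (1 − 0.818) = 5.5. About 384 × 0.10 = 38 evaluable Arm A children are undocumented. When documentation was unrelated to delivery at this rate, the simulated proportion centred near zero (median −0.02) but ranged from −1.32 to 1.19, and 14.5% of trials exceeded 50%. Near-determination therefore costs precision. The upward bias comes from the link with delivery.

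**Adding delivery to the model.** With true delivery in the outcome model, the medians were −0.02 to 0.04. The 95% simulation ranges stayed wide: −0.69 to 0.72 at best and −1.44 to 1.53 at worst.

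**The case against.** The best defence is that the plan describes a multi-path analysis. Models include causally preceding variables, a path through implementation outcomes is named, and adjusting for delivery removes the bias in the illustration. Figure 4.2.1 was not reproduced in the copy I worked from and may place delivery upstream of documentation. This stands as a reason why a repair is possible. It does not rescue the sentence: the text does not commit to that adjustment, the prescription measure in Section 8.1.3 comes from the same EMR record, and the adjusted estimate is still very imprecise.

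Other limits also stand. The plan says a high proportion will suggest efficacy, as an example and without a threshold; it does not claim proof. Only two of the four items concern delivery, and a recorded no counts as complete, so the proxy is imperfect. The illustration uses a yes/no mediator per child, whereas Table 8.1.1 lists EMR documentation at practice level as a percentage. The same argument would apply across practices, with only nine Arm A values, but the percentages above would not carry over.

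A reader might infer more than the documents support:

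- *The 20% audit leaves the mediator unknown for most controls.* About 77 of 384 evaluable Arm B children (0.20 × 384) would be audited. But the selection is random, and if the items are hidden or absent, the other values are close to known.
- *The error passes into the tool kit.* The tool-kit paragraph of Section 12.4 lists trial effectiveness, process outcomes and interviews as inputs, not mediation proportions.
- *Mediation should be confined to parent-level mediators.* That would drop prespecified provider and practice mediators, and nothing here counts against them.

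**Conclusion.** The point holds for the EMR documentation mediator and for the sentence that reads component efficacy from it. In the illustration, an EMR component with no effect shows an apparent proportion mediated of 29% to 78% at 80% delivery whenever documentation is related to delivery, and 0% when it is not. The size rests on assumed delivery and documentation rates, zero documentation in Arm B and no adjustment for delivery; the actual Arm A rates are still to be observed. The direction does not depend on the particular rates, provided that documentation is more often complete when delivery took place and that delivery raises attendance.

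A reader might conclude that documentation being nearly fixed by arm inflates the proportion, or that the whole mediation analysis fails. Neither follows: the first adds imprecision, and the second goes beyond this mediator. The primary comparison of the arms is not affected.

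**What to change.** In Section 12.4:

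1. Delete the sentence that infers component efficacy from a high mediation proportion.
2. State that the two-arm bundled design does not identify the efficacy of individual components.
3. Report EMR documentation as an Arm A fidelity and adoption measure, the role Section 8.1.4 already gives it.
4. If a proportion mediated by documentation is still reported, label it exploratory. Adjust for delivery measured independently of the EMR, using the parent exit questionnaires and numbered prescriptions in Sections 6.3.2 and 6.4. Observed encounters can serve as a check, since they cover only two or three per provider. Add a sensitivity analysis for sequential ignorability.
5. Keep the other prespecified parent, provider and practice mediators.

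The cost is SAP wording and, if item 4 is used, a little extra analysis on data already planned for collection. The trial gives up one exploratory claim about component efficacy.
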